3.1.3 Study Stopping Criteria/Holding Criteria/Dose Escalation Process

There will be a review of the study data by the DMC when there is a reasonable possibility that the investigational vaccine caused any of the listed following adverse events based on the assessment of the Investigator in one or more participants at any dose. Vaccinations will be held pending this review:

- Death
- Life-threatening adverse event or life-threatening suspected reaction
- Serious suspected adverse reaction

- Suspected, unexpected, serious adverse reaction (SUSAR)
- Acute allergic reaction or anaphylactic shock following the administration of vaccine investigational product
- Anaphylaxis or bronchospasm, indicative of an immediate hypersensitivity reaction to study vaccine
- If any participant has any of the following:
 - ALT or AST >8 x upper limit of normal (ULN)
 - ALT or AST >5 x ULN for more than 2 weeks
 - ALT or AST >3 x ULN and (total bilirubin >2 x ULN or INR >1.5)
 - ALT or AST >3 x ULN with the appearance of fatigue, nausea, vomiting, right upper quadrant pain or tenderness, fever, rash, and/or eosinophilia (>5%)

The competent authority and Research Ethics Committee (REC) will be notified of a temporary halt within 15 days according to the local requirements. If, following the review of data, a recommendation is made by the DMC to resume study enrolment and vaccine administration, the DMC will record their judgment in a memorandum to the study file and notify the Sponsor. The DMC memorandum will be forwarded to the local Medical Monitor and Investigators.

3.1.4 *Duration of Study*

3.1.4.1 *Duration for Each Participant*

Cohorts 1-4: Up to 8 months (up to 1.5 months for screening and 6.5 months on the study with study vaccine given on Day 0).

Cohorts 5 and 6: Up to 4.5 months (up to 1.5 months for screening and 3 months on the study with study vaccine given on Day 0).

3.1.4.2 *Duration of Study*

It is planned that the study will take 16 months to implement, enrol and read out.

The end of the study is defined as the date of database lock.

3.2 *Discussion of Study Design*

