This is a first in human study of the ChAdOx1 vaccine and is designed to assess the safety in both healthy adults, as well as in the target CHB population. As T cell responses to natural infection are blunted or exhausted in participants with CHB, it will be important to determine how responses in CHB compare to healthy participants. Given the uncertainty around prior use of a vectored vaccine resulting in anti-vector responses, this study will also assess the response of healthy participants who have previously received AZD1222 to ChAdOx1-HBV.

In CHB participants, low dose of the vector (selected based on doses given in a large number of other studies (NCT03399578, NCT03203421, NCT01818362, NCT01623518 and NCT03815942), will first be evaluated to minimise the risk that immune responses generated by vaccination do not result in liver toxicity. To further minimise this likelihood, only those participants whose DNA levels are well controlled on antivirals will be included in the study, and those with advanced liver fibrosis or cirrhosis will be excluded. After safety review, a higher dose, but one shown to be safely used in many other ChAdOx1 studies (HIV, malaria, influenza, MERS), will then be given. Dose selection for future studies will be based on safety

and the induction of T cell activity, as measured by both magnitude of response as well as functionality.

Hepatitis B biomarkers will be evaluated as the basis for future comparison and to assess potential efficacy.

The study will be used as a first step prior to the evaluation of a combination vaccine approach using ChAdOx1-HBV combined with both a MVA encoding the same genetic insert, with or without a low dose PD-1 inhibitor.

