3.3 Benefit Risk Assessment

There are potential known and unknown risks associated with vaccination. With any vaccine, including those that are licensed, there is a rare risk of anaphylaxis which can be fatal. All participants will be observed in the clinic for at least 30 minutes post-vaccination.

Intramuscular injection of vaccines frequently causes the local and systemic signs and symptoms that are being collected as adverse events. These will be solicited from the participant to ensure they are not occurring more frequently or are more severe than expected based on previous experience with the same or similar viral vectors.

With any new treatment there is always a possibility of an unexpected adverse events.

The administration of ChAdOx1-HBV in this study may interfere with the effectiveness of other vaccines subsequently administered to the participant. The ChAdOx1 vector induces anti-vector immunity in addition to an antigen-specific immune response. Of particular concern are neutralising antibodies directed against the capsid structure of the vector, which may have a negative effect on subsequent immunisations with the same or related adenoviral vector by neutralising the vector before it has a chance to transduce target cells. This effect decreases with longer interval between the vaccines [28,29]. In particular, there is a concern that the ChAdOx1-HBV administered in this study could decrease the response to the AstraZeneca COVID-19 vaccine, which has the same viral vector, especially if it is administered within 3 months of ChAdOx1-HBV. The Janssen (Johnson & Johnson) COVID-19 vaccine is also made with an adenovirus, and some interference cannot be ruled out. Therefore, it is recommended that participants in this study receive an alternative type of COVID-19 vaccine, such as an mRNA or protein vaccine, at least 2 weeks before and after ChAdOx1-HBV in this study.

There are also routinely scheduled reviews of safety and efficacy data throughout the study by the SMC. Stopping and holding rules have been defined for the study (see [Section 3.1.3](#)) and a DMC will perform a review of safety data if one of these is met.

Although this is the first time ChAdOx1-HBV has been administered to humans, the ChAdOx1 vector has been widely administered for many pathologies without significant safety concerns (see [Section 1.4](#)). Further detail is provided in the Investigator's Brochure.

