- Screening FibroTest >0.48 and AST to platelet ratio index of >1

In the event of discordant results between non-invasive methods, the Fibroscan result will take precedence.

21. ALT $>3 \times$ ULN, INR >1.5 unless the participant was stable on an anticoagulant regimen affecting INR, albumin <35 g/L, total bilirubin >34.2 μ mol/L, platelet count $<100 \times 10^9$ /L
22. A history of liver decompensation (e.g. ascites, encephalopathy or variceal haemorrhage)
23. Prior or current hepatocellular carcinoma
24. Chronic liver disease of a non-HBV aetiology
25. Any herbal supplements and or other medicines with potential liver toxicity within the previous 3 months prior to enrolment into this study

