Unsolicited adverse events are other events meeting the criteria for adverse events (see [Section 8.2.1](#)) apart from those the participant is specifically asked about. Unsolicited

¹ In the event that they persist longer than 3 days then an adverse event will be recorded

non-serious adverse events will be collected from the date the informed consent is signed to 28 days post-vaccination. Hospitalisations, other SAEs and AESIs will be collected for the duration of the study.

Participants will collect unsolicited adverse events in the eDiary and these will be reviewed during clinic visits with the participant and relevant information (event term, start and end date, severity, causality, outcome and seriousness) collected and entered into the eCRF as described in [Section 8.2.3](#).

7.3.2 *Laboratory Safety Tests*

Laboratory safety tests will be performed at each of the timepoints according to [Table 2](#), as per [Sections 7.1.4.1](#) and [7.1.4.2](#). Extra laboratory safety tests may be performed if the Investigator deems them to be necessary to fully evaluate an adverse event. In the event that the Investigator elects to order non-protocol-specified laboratory tests, the Investigator must record the rationale for the tests and a determination of clinical significance of the result in the source documents. The Investigator must keep the local Medical Monitor informed of adverse events of clinical significance.

Abnormal results and findings will be discussed as applicable with the participant, and the participant will be referred for follow-up with their healthcare provider if necessary.

Results from the LFTs obtained on the study must be reviewed by the Investigator (or a designee who is a medically qualified study team member) and managed in accordance with the study centre procedures. The clinical significance of all results outside of the normal range will be determined by the Investigator and may be reported as an adverse event at the discretion of the Investigator.

7.3.3 *Physical Examination*

A skin, respiratory, cardiovascular, abdominal and lymphatic system examination will be performed at screening and pre-vaccination on Day 0. A symptom-directed physical examination will be performed at all other clinic visits if required. Results will be recorded as normal, abnormal and not clinically significant or abnormal and clinically significant.

7.3.4 *Vital Signs*

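### Protocol 3.1.3 leaves unclear whether its four ALT/AST holding limits apply on the result alone or only when the Investigator suspects the vaccine

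*Protocol*

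**What the plan says.** The rule is in protocol 3.1.3. One lead sentence calls for DMC review "when there is a reasonable possibility that the investigational vaccine caused any of the listed following adverse events based on the assessment of the Investigator", and the next makes the vaccination hold last until that review. A bulleted list follows: death, life-threatening events, serious suspected reactions, SUSARs, allergic reactions and, last, a liver item. The liver item is built differently. It opens "If any participant has any of the following" and gives four limits:

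- ALT or AST above 8 x ULN
- ALT or AST above 5 x ULN for more than 2 weeks
- ALT or AST above 3 x ULN with total bilirubin above 2 x ULN or INR above 1.5
- ALT or AST above 3 x ULN with listed symptoms or eosinophilia

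None of the four mentions causality. The same section says the competent authority and REC "will be notified of a temporary halt within 15 days according to the local requirements".

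Protocol 3.3 adds that "a DMC will perform a review of safety data if one of these is met", referring back to 3.1.3. On liver tests generally, 7.3.2 says "Results from the LFTs obtained on the study must be reviewed by the Investigator" or a medically qualified designee. It adds that the clinical significance of out-of-range results "will be determined by the Investigator and may be reported as an adverse event at the discretion of the Investigator".

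**The concern.** Protocol 3.2 explains that CHB participants receive the low dose first "to minimise the risk that immune responses generated by vaccination do not result in liver toxicity". The four limits are the protocol's numeric holding rule for that risk. If the lead sentence governs them, one Investigator's causality judgement, made in an open-label trial, decides whether dosing must stop and whether the independent committee must see the case. If the bullet stands alone, the laboratory result decides. Staff at two centres could follow the same text in good faith and act in opposite ways on the same result.

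**Working it through.** No arithmetic settles this. The check is to set the two readings side by side and then look for any other provision that chooses between them or closes the gap.

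**Step 1. The two readings.**
- Lead-sentence reading: trigger = (limit exceeded) and (Investigator finds a reasonable possibility of vaccine causation).
- Stand-alone reading: trigger = (limit exceeded).

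| Non-serious ALT/AST result | Lead-sentence reading | Stand-alone reading |
|---|---|---|
| Over a limit, judged related | DMC review and hold | DMC review and hold |
| Over a limit, judged unrelated | Neither obliged | DMC review and hold |
| Under all four limits | Not triggered | Not triggered |

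The readings differ only in the middle row, and there they give opposite actions.

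**Step 2. Does another section choose between them?** Protocol 3.1.1, 3.3 and 8.1.5 and SAP sections 6 and 6.4 refer to the stopping or holding rules without restating the liver limits. The 24-hour notice to the DMC (8.1.5) and the convening of the SMC when a rule is met (8.1.4) depend on the same rules, so they inherit the ambiguity.

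**Step 3. Does another safeguard oblige review or a hold in the middle row?**
- The Investigator may pause dosing (8.1.1), but this is optional and rests on suspicion of the vaccine.
- The Local Medical Monitor reviews safety information (8.1.3). The Sponsor and the Monitor may add a causality opinion (8.2.3.2), but 3.1.3 names only the Investigator's assessment.
- The SMC must promptly review severe local or systemic reactions and vaccine-related SAEs, and it may hold the study (8.1.4). Even if a laboratory rise counts as a severe reaction, this is an SMC review with a discretionary hold. The SMC is made up of the Sponsor Representative, the Principal Investigators, the Local Medical Monitor and the Chief Investigator. Only the DMC is specified as independent (8.1.5).
- Contacting the DMC chair in other situations is optional (8.1.5).
- Scheduled SMC reviews may take place from 48 hours after dosing, whereas the first post-dose liver tests are on Day 7. No SMC review is scheduled after cohort 3 dosing is complete, and none is required for cohorts 5 and 6 (3.1.1, 8.1.4).

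For a non-serious rise judged unrelated, none of these obliges a DMC review or a hold.

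**Step 4. How much is exposed?** All 4 limits sit under the lead sentence. Each participant has one dose, on Day 0, so a hold protects only those not yet dosed. Among the 12 planned CHB participants, ignoring replacements, that is between 0 and 11 (12 - 1 = 11), plus any undosed healthy participants. The documents give no CHB dosing intervals, so the range cannot be narrowed. They also give no basis for estimating how often a breach would be judged unrelated.

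**The case against.** The strongest reply is that the bullet's own wording favours the stand-alone reading. A conditional clause about laboratory limits cannot itself be an adverse event that the vaccine caused, and speaking of rules as met suits a numeric threshold. That is right as a reading of the bullet, and the sponsor may already work that way. It does not settle the matter, because the bullet still sits in a list governed by a sentence that says otherwise.

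A second reply is that a causality gate is a legitimate design choice. It applies to every item in the list, including death, and 8.2.3.2 reserves the unrelated category for events with no reasonable possibility of causation and other, more likely causes. This also stands, and it is why the exposed case is narrow. Even so, if a gate on the liver limits is intended, the bullet should say so.

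Two stronger readings are tempting, and the documents do not support them.

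- A reader might infer from 7.3.2 that a breach could escape by never being called an adverse event. Section 8.2.1.1 largely answers this: Grade 3 or symptomatic results usually are adverse events. In SAP Appendix 1, ALT or AST above 5 x ULN is at least Grade 3. Bilirubin above 2 x ULN with raised transaminases passes the Grade 4 cut-off of 1.75 x ULN. Most of the fourth limit is defined by symptoms. Only the INR branch and the eosinophilia-only branch are not clearly covered.
- A reader might infer from the entry cap on ALT in exclusion criterion 21 that a causality gate has no purpose. The cap covers ALT but not AST, and only CHB participants. It also says nothing about causes that arise after entry, which a causality assessment is there to weigh.

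**Conclusion.** The point holds as an internal inconsistency in a safety rule, and it should be corrected. On the lead sentence as written, a non-serious ALT/AST result over any of the four limits that is judged unrelated obliges neither DMC review nor a hold. On the more natural reading of the bullet, it obliges both. The protocol and SAP do not say which applies.

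The documents do not show that such a result would go unacted on. Discretionary routes to stop dosing remain, and the SMC and DMC charters, which were not available, may already resolve the question. The conclusion therefore concerns the protocol and SAP text only and is held with medium confidence.

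**What to change.** Take the four liver limits out of the causality list in 3.1.3 and give them their own sentence. It should say that any post-vaccination result meeting a limit is notified to the DMC within the 24 hours already set in 8.1.5. It should also say that participants not yet dosed are held pending the DMC's review, whatever the Investigator's causality or adverse event classification.

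The INR arm of the third limit needs an exception where a stable anticoagulant regimen explains the raised INR. Exclusion criterion 21 already makes this allowance for CHB participants: "ULN, INR >1.5 unless the participant was stable on an anticoagulant regimen affecting INR". The bilirubin arm and the other three limits would still apply to such a participant. The charters should be matched to the new text if they differ.

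No new visits, tests or committee are needed. The cost is an occasional DMC review, dosing pause and temporary-halt notification for a rise that proves unrelated. Changing a holding rule is also probably a substantial amendment under 13.5, which in general needs approval before it takes effect. If dosing is already complete, the sponsor should state which reading was applied and use the corrected wording in the follow-on study foreseen in 3.2.

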3.3 Benefit Risk Assessment

There are potential known and unknown risks associated with vaccination. With any vaccine, including those that are licensed, there is a rare risk of anaphylaxis which can be fatal. All participants will be observed in the clinic for at least 30 minutes post-vaccination.

Intramuscular injection of vaccines frequently causes the local and systemic signs and symptoms that are being collected as adverse events. These will be solicited from the participant to ensure they are not occurring more frequently or are more severe than expected based on previous experience with the same or similar viral vectors.

With any new treatment there is always a possibility of an unexpected adverse events.

The administration of ChAdOx1-HBV in this study may interfere with the effectiveness of other vaccines subsequently administered to the participant. The ChAdOx1 vector induces anti-vector immunity in addition to an antigen-specific immune response. Of particular concern are neutralising antibodies directed against the capsid structure of the vector, which may have a negative effect on subsequent immunisations with the same or related adenoviral vector by neutralising the vector before it has a chance to transduce target cells. This effect decreases with longer interval between the vaccines [28,29]. In particular, there is a concern that the ChAdOx1-HBV administered in this study could decrease the response to the AstraZeneca COVID-19 vaccine, which has the same viral vector, especially if it is administered within 3 months of ChAdOx1-HBV. The Janssen (Johnson & Johnson) COVID-19 vaccine is also made with an adenovirus, and some interference cannot be ruled out. Therefore, it is recommended that participants in this study receive an alternative type of COVID-19 vaccine, such as an mRNA or protein vaccine, at least 2 weeks before and after ChAdOx1-HBV in this study.

There are also routinely scheduled reviews of safety and efficacy data throughout the study by the SMC. Stopping and holding rules have been defined for the study (see [Section 3.1.3](#)) and a DMC will perform a review of safety data if one of these is met.

Although this is the first time ChAdOx1-HBV has been administered to humans, the ChAdOx1 vector has been widely administered for many pathologies without significant safety concerns (see [Section 1.4](#)). Further detail is provided in the Investigator's Brochure.

As this is a first in human study without prior clinical data there may be no benefit to study participants. The participants in the CHB groups will however receive additional monitoring of their HBV status compared to the standard of care.

4 STUDY POPULATION

4.1 Number of Participants

It is planned that 40 healthy participants and 12 participants with CHB infection and virally suppressed with oral antiviral medication will be enrolled in the study. Chronic HBV participants will be recruited/deemed eligible by hepatologists, infectious disease specialists or physicians experienced in treating CHB participants. Centres not meeting the enrolment expectations will be considered for replacement with or addition of a new site. If participants leave the study before all follow-up visits are completed (for any reason), then these may be replaced at the discretion of the study team. A log of all participants enrolled into the study (i.e. having given informed consent) will be maintained in the Investigator's Site File (ISF) at the study centre irrespective of whether they have treated with vaccine or not.

A total of 10 healthy participants and 12 participants with CHB infection is considered sufficient to confirm the safety, tolerability and immunogenicity of ChAdOx1-HBV and to answer the objectives of the study before progressing to larger studies. An additional 30 healthy participants (15 who have received two doses of AZD1222 and 15 who have received at least two doses of either Pfizer or Moderna mRNA COVID-19 vaccine) will be recruited to assess whether prior receipt of AZD1222 results in decreased T cell responses to ChAdOx1-HBV.

The statistical considerations used to determine the number of participants planned and evaluable are presented in [Section 10.1](#).

4.2 Inclusion Criteria

Participants must meet *all* the following criteria to be eligible for the study:

1. Adult males or females aged ≥ 18 to ≤ 65 years at screening
2. Body Mass Index $\leq 30 \text{ kg/m}^2$
3. Able to provide informed consent indicating they understand the purpose of, and procedures required, for the study and are willing to participate
4. If female, willing not to become pregnant up to 8 weeks after last dose of study vaccine, not breast feeding
5. If female: Not pregnant and one of the following:
 - Of non-childbearing potential (i.e. women who have had a hysterectomy or tubal ligation or are post-menopausal, as defined by no menses in ≥ 1 year)
 - Sexual abstinence, only if the participant refrains from heterosexual intercourse during the entire study period and it is the usual lifestyle of the participant
 - Of childbearing potential but agrees to practice highly effective contraception for 4 weeks prior to study vaccine and 8 weeks after study vaccine. Highly effective methods of contraception include one or more of the following:
 - Male partner who is sterile (medically effective vasectomy) prior to the female participant's entry into the study and is the sole sexual partner for the female participant
 - Combined (estrogen and progestogen containing) hormonal contraception associated with inhibition of ovulation:
 - oral
 - intravaginal

- transdermal
- Progestogen-only hormonal contraception associated with inhibition of ovulation:
 - oral
 - injectable
 - implantable
 - An intrauterine device
 - Bilateral tubal occlusion

Healthy participants (cohorts 1 and 2):

6. Considered to be healthy with no current conditions that may significantly impair participant safety or influence study results, in the opinion of the Investigator

Participants with well controlled CHB (cohorts 3 and 4):

7. Documented evidence of chronic HBV infection (e.g. HBsAg positive ≥ 6 months with detectable HBsAg levels at screening)
8. Receipt of only either entecavir or tenofovir for at least 12 months before screening
9. Virally suppressed (HBV DNA <40 IU/mL for ≥ 6 months)
10. HBsAg <10000 IU/mL

Healthy participants (cohort 5):

11. Considered to be healthy with no current conditions that may significantly impair participant safety or influence study results, in the opinion of the Investigator
12. Adult males or females aged ≥ 40 to ≤ 60 years at screening
13. Completed second dose of COVID-19 AZD1222 vaccine 10 to 18 weeks before enrolment

Healthy participants (cohort 6):

14. Considered to be healthy with no current conditions that may significantly impair participant safety or influence study results, in the opinion of the Investigator
15. Adult males or females aged ≥ 40 to ≤ 60 years at screening
16. Received the latest dose of either Pfizer (Comirnaty®) or Moderna (Spikevax) mRNA COVID-19 vaccine 6 to 30 weeks before enrolment

